Participants at UMFCD are recruited through general practitioners (GPs). At a GP visit, if inclusion/exclusion criteria and willingness to participate are confirmed, women **50-70** years old can be sent for screening in specialised centres (external, different centres, public or private). Only those women attending a mammography or an ultrasound test are suitable for participation. If inclusion/exclusion criteria and willingness to participate are confirmed, an in-person appointment for ICF signature is scheduled.

Colorectal cancer:

Participants at UMFCD are recruited through general practitioners (GPs). At a GP visit, if inclusion/exclusion criteria and willingness to participate are confirmed, individuals 50-70 years old can be sent for screening in specialised centres (external, different centres, public or private). Only those individuals attending a FOBT or a colonoscopy are suitable for participation. If inclusion/exclusion criteria and willingness to participate are confirmed, an in-person appointment for ICF signature is scheduled.

Common:

After ICF signature, participants are centrally randomised through REDCap, ²⁹ and, if assigned to the experimental group (EG), the iBeChange app is downloaded together with a step-by-step demonstration on its functionalities by the researcher.

If assigned to the iBeChange group, the participant is asked for their willingness to use the study wearable. If yes, a specific ICF for wearables is signed and the participant is randomised to receive or not the wearable. If assigned to the wearable sub-group, and the needed size is available, the Oura smart ring is delivered (EGw).

The step-by-step demonstration of iBeChange will be detailed in a standardised protocol for welcoming and introducing the app to participants across all centres, considering age and other factors.

For enrolled participants of all groups, questionnaires will be sent by email through the REDCap platform. These will include demographic variables as well as questionnaires for assessing primary and secondary outcomes. These questionnaires are designed for the participant to answer at home, not in the recruitment centre.

Intervention for the iBeChange participants will start as soon as they provide enough information in the app for it to recommend a health pillar and deliver personalised interventions. For further details, please visit section 6.2.

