6.1. Control group (CG) intervention

The control intervention consists of receiving an **informative leaflet** with a **summary of the clinical recommendations for cancer prevention**.

This document already exists in the ICO cancer screening program and will be adapted to Italian and Romanian for use in IEO and UMFCD, respectively. An English version can be found in Annex 10.1. To standardise this intervention, the translated informative leaflet will be delivered to control participants at each centre in their national language after randomisation.

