6.5. Measures to minimise bias: randomisation and blinding

Participants will be randomised into either the control or the iBeChange group, with stratification based on recruitment centre and cancer screening type.

For those in the iBeChange group, participation in the wearable sub-study will be optional. To prevent selection bias, participants who opt in will undergo a second randomisation to determine whether they receive the wearable device or not.

Due to the nature of the intervention—where only the experimental group receives a digital behavioural change program—blinding is not feasible in this pilot study. However, to minimise bias in outcome assessment, all evaluations will be conducted remotely, ensuring that responses from participants in both groups are collected without direct influence from healthcare professionals.

7. Data Flow, management and protection

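### Self-reported baseline outcomes are answered at home after the arm is known, which puts every secondary estimate that uses them at risk of bias

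*Protocol*

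**What the plan says.** Section 5.2 (the part common to all centres) sets the order of events:

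- **Allocation.** "After ICF signature, participants are centrally randomised through REDCap".
- **Experimental group, same appointment.** "the iBeChange app is downloaded together with a step-by-step demonstration on its functionalities by the researcher". Participants in the wearable sub-group also receive the ring.
- **Outcome questionnaires.** "For enrolled participants of all groups, questionnaires will be sent by email through the REDCap platform". They are not filled in at the visit: "These questionnaires are designed for the participant to answer at home, not in the recruitment centre".
- **Start of intervention.** "Intervention for the iBeChange participants will start as soon as they provide enough information in the app for it to recommend a health pillar". The REDCap baseline is not a condition.

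Other sections fit this order:

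- **Section 6.1 (control group).** "the translated informative leaflet will be delivered to control participants at each centre in their national language after randomisation".
- **Table 2.** Randomisation sits in the in-person Screening Day 0 column. The behavioural, psychosocial and cost outcomes sit under Time 1 Baseline, Day 0, with no window and no stated order relative to randomisation.
- **Section 7.2.1.** It runs from consent to randomisation to registration by group, and then describes the questionnaires separately for each group.
- **Section 6.2.** The app begins by asking about smoking, alcohol, nutrition, physical activity and emotional well-being, and shows the user scores against cancer-prevention guidelines.
- **Section 6.5.** "blinding is not feasible in this pilot study". The stated safeguard is remote evaluation, so that professionals do not influence the answers.

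**The concern.** A baseline is useful for adjustment because allocation cannot have affected it. Here it can have. When participants open the emailed questionnaire they know their arm. Those in the experimental group have also seen the app demonstrated and may already have answered similar questions in it and seen their habits scored. Knowing the arm or seeing the scores could change what they report as baseline, and could change whether they return it. Remote completion deals with influence from staff, not with the participant's own knowledge.

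Effectiveness is measured at only two time points, baseline and week 12 (section 4.4), so baseline is one of two observations in the longitudinal model of section 8.5. An allocation-induced difference at baseline would pass into any estimate that uses it. The estimates have further uses: section 8.6 applies efficacy and futility rules to the treatment effect, and section 8.8 takes effect sizes from the pilot to revise the RCT sample size. No later analysis can recover a pre-randomisation baseline that was never collected.

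**Working it through.** **1. Is there any text that puts baseline before allocation or app use?** Sections 5.2, 6.1, 6.2, 6.5 and 7.2.1 and Table 2, read together, contain none. Table 3 says measures will be taken before and after the intervention, but section 5.2 lets the intervention start on app data alone. Nothing enforces the order that Table 3 assumes.

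**2. Which outcomes are affected?** Section 4.4 names six main secondary measures. Five are self-reported: cigarettes per day, weekly alcohol, processed food and red meat, minutes of activity, and PSS-4. The sixth is BMI. Section 4.3 lists height and weight for the initial in-person interview, Table 2 lists them under Time 1, and section 5.2 says the emailed questionnaires include demographic variables. Baseline BMI may therefore be exempt, but these three places do not agree. The baseline EQ-5D-5L and resource-use items are also collected at Time 1.

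**3. Size, as an illustration.** The protocol gives no figure to reproduce. Inputs:

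- 90 per group (section 8.2).
- d, the shift in experimental-arm baseline answers caused by allocation or app feedback: **assumed**, 0 to 0.2 SD.
- ρ, the baseline/week-12 correlation: **assumed**, 0.3 to 0.7.
- Outcomes in SD units with equal variances.

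Formulas, for a week-12 difference Δ and an observed baseline difference with expectation d:

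- Week 12 alone: estimate Δ, bias 0, SE = √(2/90) = 0.149.
- Change score: Δ minus the baseline difference, bias −d, SE = 0.149 × √(2(1−ρ)).
- Baseline-adjusted: Δ minus ρ times the baseline difference, bias −ρd, SE = 0.149 × √(1−ρ²).

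| ρ | d | Change-score bias (SE) | Adjusted bias (SE) |
|---|---|---|---|
| any | 0 | 0 | 0 |
| 0.3 | 0.1 | −0.10 (0.18) | −0.03 (0.14) |
| 0.3 | 0.2 | −0.20 (0.18) | −0.06 (0.14) |
| 0.5 | 0.1 | −0.10 (0.15) | −0.05 (0.13) |
| 0.5 | 0.2 | −0.20 (0.15) | −0.10 (0.13) |
| 0.7 | 0.1 | −0.10 (0.12) | −0.07 (0.11) |
| 0.7 | 0.2 | −0.20 (0.12) | −0.14 (0.11) |

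The signs are for a positive d; a negative d reverses them.

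**4. Check by simulation** (4,000 runs per setting, true effect 0.30 SD). At d = 0.2 the adjusted bias was −0.061, −0.095 and −0.140 for ρ = 0.3, 0.5 and 0.7, and the change-score bias was −0.200, −0.194 and −0.200. The week-12-only estimate was within 0.007 SD of the truth in every setting. With d = 0, which is what a pre-randomisation baseline would secure, no estimator was off by more than 0.005 SD.

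**The case against.** Several points on the other side are sound.

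- **Feasibility is primary.** Section 8.1 says the focus is not formal testing of efficacy. Consent rate, timelines, usability and wearable adherence are not biased by the order of baseline and allocation. This stands and limits the seriousness.
- **The shift is assumed.** The documents give neither d nor ρ, and d = 0 is consistent with them. This stands: they show a risk, not a bias of known size or direction.
- **The analysis may avoid the problem.** Section 8.5 does not say how baseline enters the model, and that detail may properly sit in a SAP. So it is unknown whether the change-score or the adjusted column applies. Neither is free of the problem if d is not zero.
- **Baseline is scheduled for Day 0.** On the written schedule, app exposure before it would be brief. But no window or lock enforces this, and knowledge of the arm precedes it in any case.
- **Home completion has a purpose.** It keeps professionals from influencing answers, and it would be harmless if it came before allocation. The defect is the missing order, not the place.

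A reader might infer that every effectiveness estimate is biased, or that baseline non-response will differ by arm. The documents do not support either. A week-12-only comparison does not use the baseline, the others are biased only if answers or non-response differ by arm, and arm-dependent non-response is a possibility that has not been shown. Bias from unblinded self-report at week 12 is a separate matter.

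**Conclusion.** The point holds as a design weakness in the secondary objectives. Followed as written, section 5.2 yields a self-reported baseline taken after the arm is known and, in the experimental group, after the app is installed and possibly used. Secondary effectiveness and cost-effectiveness estimates that rely on that baseline are at risk of bias, and so are the interim rules and RCT effect sizes derived from them.

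Under the assumptions above, the bias in absolute terms ranges from zero to about 0.14 SD for an adjusted estimate (SE about 0.11 to 0.14) and from zero to 0.20 SD for a change score (SE about 0.12 to 0.18). Section 8.3 calls 0.2 SD a small effect, so the upper end is of that order. The direction is unknown. The protocol should be corrected, but the flaw does not undermine the primary feasibility aims.

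**What to change.** In section 5.2 and Table 2 (and in the flow figures, if they show the same order), state this sequence: consent; REDCap baseline completed by the participant unaided; randomisation released by REDCap only once the baseline is submitted; then app demonstration or leaflet. Sites could do this in either of two ways:

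- on a phone or tablet at the visit; or
- by an emailed link after consent, with allocation released on return. This keeps the remote completion that section 6.5 relies on.

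If a site can do neither, the minimum is to lock app activation until the baseline is submitted, record timestamps for baseline and first app use, report baseline non-response by arm, and add a sensitivity analysis of week-12 values that leaves the baseline out. This removes app exposure before baseline but not knowledge of the arm.

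Also reconcile section 4.3, section 5.2 and Table 2 on when and how baseline height and weight are obtained, and whether that is before randomisation.

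**Cost.** The visit option lengthens Day 0. The battery is not short, and at IEO consent is taken at the screening appointment itself. The email option delays allocation a little, and the demonstration, which now takes place at the consent appointment, would need a later contact. The sample size of 180 and the protocol's other stated figures do not change.

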			Perceived Stress: Perceived Stress Scale (PSS-4)
			Anxiety and Depressive symptoms: Patient Health Questionnaire (PHQ-4)
			Perceived Social Support: Perceived Social Support (F-SozU K-3)
			Cost-effectiveness:
			Cost-effectiveness PECUNIA Resource Use Measurement (PECUNIA RUM) Instrument
			EQ-5D-5L Quality of Life
Tertiary/Explora	tory		
Voice analysis			
To assess the feasibility of using voice biomarkers to derive information about emotional distress	Preliminary concurrent validity (accuracy of machine learning algorithm on voice signals to automatically classify emotional distress)	Achieving a high accuracy of machine learning algorithms is essential to confirm that voice signals can be used as valid biomarkers of emotional distress.	Voice recordings (raw data) Emotional distress thermometer
Wearable Sub-stud	у		1
To test the feasibility and suitability of wearables to complement psychosocial and behavioural features in a health intervention. To assess the correlation between wearable data	• Feasibility assessed through the completion rate of wearable data collection and the percentage of successful data transmissions without technical issues. The times a ring size is not available at site for a participant	Assessing data completion rates and successful transmissions demonstrates whether wearables can reliably collect and transfer data to support the intervention. Data from wearables logistics will allow to adjust ring size purchases and distribution among clinical sites. Investigating participant	Physical activity: number of steps; metabolic equivalent of task (MET) (1-minute intervals); average MET minutes (average MET level sustained throughout the day, factoring in all activities and rest periods); high activity MET minutes and High activity time; low activity MET minutes and low activity time; medium

Objectives	Endpoints	Justification for endpoints	Collected measures

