and self-reported measures. To assess whether wearable data can improve the effectiveness of personalised recommendation s delivered by the recommender system in the intervention in future settings. To compare user's adherence and usability of the system between participants in the wearable substudy and those in the standard iBeChange group.	will also be registered Suitability evaluated via participant-reported satisfaction and perceived ease of use of wearables, measured through post-intervention questionnaires. Preliminary concurrent validity (correlation between wearable data with self-reported outcome measures in domains such as physical activity and psychosocial health). Changes in primary and secondary outcomes between participants in the wearable sub-study and the standard iBeChange group to evaluate the preliminary impact of the use of wearables on the intervention. Changes in satisfaction and adherence rates between participants in the wearable on the intervention.	ease of use helps determine if wearables are suitable for complementing the monitoring of psychosocial and behavioural health. Validating the correlation between wearable data and self-reported measures is essential to confirm that wearables can assess psychosocial and behavioural constructs. Comparing changes between groups helps evaluate whether wearables, by providing objective and timely data, can enhance the personalisation and effectiveness of the iBeChange intervention. Analysing usability and adherence reveals whether the use of wearables increases participant engagement, positively impacting their involvement in the intervention.	medium activity time; sedentary MET minutes and sedentary time; inactivity alerts; active calories (calories burned during physical activity); total calories (total number of calories burned during the day) • Psychosocial health: • Sleep data: heart rate; heart rate variability; latency (time it takes to fall asleep from the moment the subject gets into bed); temperature deviation; restless period; average breath; efficiency (ratio of time actually spent sleeping to the total time spent in bed); sleep score; light, deep and REM sleep time; readiness score (body's recovery status and physical preparedness); startend bed time. • Stress Resilience: daytime stress (in terms of heart rate, heart rate variability, motion and temperature throughout the day). • Satisfaction and usability of smart ring use

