Participants will also be asked for optional consent of voice recordings to analyse potential vocal stress markers. This will be registered and the option to record within the iBeChange app will only be displayed to those participants in the experimental group that have consented.

Regarding wearables, the ICF signature appointment and the introduction to the iBeChange app will also be used to deliver the device. The consumer-grade Oura ring has been selected. A stock of devices will be available at each recruitment centre. An Oura ring of the participant's size will be delivered and connected to the participant's iBeChange app account.

In case the needed size is not available at one centre, it will be requested at the other sites, and that participant will be excluded from the wearable sub-study so as not to delay the start of the intervention delivery.

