6.3. Experimental sub-group intervention: Wearable Sub-study (EGw)

Participants randomised to the experimental group will be offered the opportunity to join the wearable sub-sample until the required sample size is reached in each clinical centre. If participants agree, and after specific ICF signature, a second randomisation will take place to determine whether they are assigned to the wearable sub-sample or not. Participants assigned to the wearable sub-sample will be provided with an **Oura ring** of their size, and additional data will be collected from these participants.

A potential issue is that, despite purchasing ring sizes based on the most likely gender- and age-specific measurements of the recruited sample, there may still be instances where suitable sizes are not available for participants willing to join this subsample and assigned to the wearable sub-group. To address the potential unavailability of ring sizes for participants assigned to the wearable sub-group, several measures will be implemented. Firstly, the extra rings will be centrally stored at one clinical centre (i.e., IEO), enabling redistribution to other centres if needed. However, fingers other than the index finger may be used without compromising data collection. Furthermore, if a suitable ring size is unavailable for a participant, the enrolment can proceed with the next eligible participant included in the iBeChange intervention group if willing to and randomised to the wearable sub-group. Lastly, if one centre completes recruitment ahead of others, any surplus rings will be reallocated to centres still actively recruiting participants.

The study will provide clear instructions for device use, offer technical support if needed, and ensure participants are fully informed about data security measures by signing a specific informed consent form. In this pilot study, participants will be able to access the Oura ring app, where the visual progress tracking will be available. This can significantly enhance participant engagement and minimise the risk of non-adherence.

Participants will be enrolled across all three clinical centres involved in the pilot study (i.e., ICO, IEO, and UMFCD). 33% of the intervention group will receive a wearable device, corresponding to approximately 30 participants across all centres (180 participants is the total recruitment of the pilot study, 60 participants per centre).

[figure not shown]

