Alongside these evaluations, we will test whether participants using wearables demonstrate a higher degree of behavioural change compared to those who did not receive the devices. To assess this, we will compare smoking, alcohol, nutrition, physical activity, and psychosocial outcomes between the wearable and non- wearable groups. For these comparisons, we will use the same statistical methods described above, including Bayesian models and exploratory analysis techniques (e.g., t-tests for between-group comparisons). These analyses will help determine whether the use of wearables leads to more significant improvements in outcomes compared to conventional methods.

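### Ring size is checked only after the second randomisation and only in the ring arm, so the exploratory ring versus no-ring comparison is not as randomised

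*Protocol*

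**What the plan says.** **Order of steps.** Section 5.2 (Common) sets the sequence after allocation to iBeChange: willingness is asked, the wearable consent is signed, and the participant is randomised to ring or no ring. Delivery then carries a condition: "If assigned to the wearable sub-group, and the needed size is available, the Oura smart ring is delivered (EGw").

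**If the size is missing.** The size is requested from the other sites, but "that participant will be excluded from the wearable sub-study so as not to delay the start of the intervention delivery" (section 5.2). Section 6.3 describes the problem among people already assigned to the ring and adds that "if a suitable ring size is unavailable for a participant, the enrolment can proceed with the next eligible participant", provided that person is willing and is randomised to the ring.

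**Mitigations in section 6.3.** Spare rings are held centrally, surplus rings are reallocated, and "fingers other than the index finger may be used without compromising data collection".

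**Purpose of the second randomisation.** Section 6.5: "To prevent selection bias, participants who opt in will undergo a second randomisation".

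**The comparison.** Section 8.7: "we will test whether participants using wearables demonstrate a higher degree of behavioural change compared to those who did not receive the devices". Table 3 in section 4.2 lists among the exploratory endpoints "Changes in primary and secondary outcomes between participants in the wearable sub-study and the standard iBeChange group". It also logs, for logistics, "The times a ring size is not available at site for a participant".

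**The concern.** An exclusion that follows randomisation and can happen in only one arm filters the two arms differently. Someone with an unstocked size leaves the sub-study if allocated a ring and stays if allocated no ring. If such people would have changed more or less than others over 12 weeks, the difference between arms moves for a reason unrelated to the ring. That partly undoes what section 6.5 says the second randomisation is for.

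The planned comparison does not repair this. Section 8.7 defines the groups by use or receipt of the device, and Table 3 by membership of the sub-study. Neither follows the allocation, and no text keeps an unfitted person in the ring arm. Read literally, someone allocated a ring but not fitted falls among those without a device and so becomes a comparator.

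At stake is the tertiary question of whether ring users change more than non-users.

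**Working it through.** **Reproducing the plan's figure.** Section 6.3 gives 33% of the intervention group, about 30 people. With 90 in that group (section 8.2): 0.33 × 90 = 29.7; and 3 centres × 10 = 30. The figure reproduces.

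**Assumptions (the protocol gives none of these).**
- 30 fitted after replacement, plus m = 1, 3 or 5 excluded, so the excluded share is p = m/(30 + m) = 0.032, 0.091 or 0.143.
- All shortages lie at one end of the size range.
- Size and 12-week change are jointly normal with correlation r = 0.1 to 0.3.
- 60, 30 or 15 opted-in comparators (nc). Sixty is a ceiling (90 − 30) that requires everyone to opt in.

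**Case A: unfitted people are dropped.** Shift in the ring arm's mean = r × φ(z)/(1 − p), where z is the upper-p point of the standard normal.

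| m | φ(z)/(1 − p) | r = 0.1 | r = 0.3 |
|---|---|---|---|
| 1 | 0.075 | 0.007 SD | 0.022 SD |
| 3 | 0.180 | 0.018 SD | 0.054 SD |
| 5 | 0.263 | 0.026 SD | 0.079 SD |

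Standard error of the contrast = √(1/30 + 1/nc) = 0.224, 0.258 or 0.316 SD for nc = 60, 30 or 15. The largest shift, 0.079 SD, is 35%, 31% or 25% of it.

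**Case B: unfitted people are counted as no-ring.** The excluded have mean r × φ(z)/p. At m = 5 and r = 0.3 that is 0.3 × 1.580 = 0.474 SD. They move the comparator mean by 5 × 0.474/(nc + 5) = 0.036, 0.068 or 0.118 SD. Adding 0.079 gives a total of 0.12, 0.15 or 0.20 SD.

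**Dependence on the shortage pattern.** Simulating Case A with 4 million draws at m = 5 and r = 0.3 gives 0.079 SD when shortages are one-sided, 0.044 SD when split 80/20 between the two ends, and 0.000 SD when split evenly.

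**Effect of the remedies.**
- Analysing as allocated removes the shift. If missing rings are never delivered, 30/(30 + m) = 97%, 91% or 86% of the ring arm has a ring, which dilutes the effect by that factor.
- A pre-check also removes the shift but leaves some opt-ins unrandomised. The ratio among opt-ins is not stated. At an assumed 1:2, 2m = 2, 6 or 10 comparators are lost, and √(1/30 + 1/(60 − 2m)) = 0.225, 0.228 or 0.231 SD, against 0.224.

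**The case against.** **Small and exploratory.** The comparison is tertiary, section 8.1 puts the statistical focus on feasibility, and its wearable hypothesis concerns days of use. With 30 ring users the detectable effect at 80% power is about 2.80 × SE = 0.63 to 0.89 SD. In Case A the worst shift is well inside the noise. This stands, and it sets the priority.

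**The mechanism is assumed.** Section 6.3 says sizes are bought to likely gender- and age-specific measurements. A reader might infer that those removed must be people with unusual sizes. The document does not establish that: a common size can also run out late in recruitment, which would depend on timing more than on build. This stands; hence the near-zero end of the range.

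**Adjustment may help.** Section 8.5 says the analysis accounts for confounding, section 8.7 applies the same methods here, and age, sex, height and weight are collected (section 4.3). The covariates are not named, and adjustment does not return an excluded participant to the comparison. It reduces the concern without removing it.

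**Other documents may settle it.** A SAP or the separate wearable deliverable (D5.2) could define an as-allocated analysis. But the protocol itself orders the exclusion and words the comparison by receipt, and an analysis rule would not change the order of steps at the visit.

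**Mitigations.** Other fingers, central stock and reallocation make shortages rarer. The protocol still expects some, since it counts them as an endpoint.

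**Conclusion.** The point holds as a minor design flaw. The exclusion follows randomisation, applies to one arm only, and is paired with a comparison defined by receipt or membership.

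Its size cannot be estimated from the protocol. Under the assumptions above it is about 0.01 to 0.08 SD if unfitted people are dropped. With 5 exclusions and a correlation of 0.3 it is about 0.12 to 0.20 SD if they are counted as no-ring. The top of that range reaches what section 8.3 calls a small effect. The shift is near zero if shortages are unrelated to outcome or fall evenly on large and small sizes. Its direction is unknown.

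Three stronger readings are not supported:
- *The main trial comparison is compromised.* It is not; the exclusion is from the sub-study only, and nothing removes these people from the experimental group.
- *Section 5.2 contradicts Figure 4.* The legend in section 6.3 mentions later receipt of a ring, but the figure is not shown and may treat exclusion and later delivery as separate branches.
- *The flaw will pass into the full RCT.* That protocol is not at hand, and the pilot is meant to change procedures before it.

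**What to change.** Either of two changes removes the differential exclusion.

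1. **Check before randomising.** At the same visit, after wearable consent, size the finger and confirm that a fitting ring (any suitable finger) is available. Randomise only those who can be fitted, add this to Table 5, and still record every unavailable size for the logistics endpoint. If a ring cannot be handed over after allocation, keep the person in the ring arm. Cost: one step moved earlier and no extra rings, but a few opt-ins are not randomised, including some who would have been allocated no ring. The standard error rises from 0.224 to at most about 0.231 SD in the scenarios shown.
2. **Keep the order and drop the exclusion in section 5.2.** Unfitted people stay in the ring arm. Nobody is lost; the price is slight dilution of the ring effect.

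With either option, reword section 8.7 and Table 3 to compare opted-in participants by allocation at the second randomisation, not by receipt. Align the wording of sections 5.2 and 6.3, and check section 5.2 against Figure 4 so that sites have one rule for a missing size.
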